1.3.2.3 Follow up period and trial completion

A follow up visit (Visit 5) will be performed 7-14 days after the last dose of trial medication. The expectation is that this visit will be performed via a telephone call, but where appropriate, a clinic visit may be scheduled. The assessments to be performed at Visit 5 are indicated in the Figure 1-2. Schedule of Assessment.

Visit 5 marks the completion of the study for the individual patient. After the completion of the study the patient will receive standard medical care.

1.3.2.4 Early discontinuation of trial medication

See Protocol (1245.148) [Section 3.3.4.1](#) for procedures to be followed in case a randomised patient does not reach Visit 4 for any reason.

1.4 Changes to the Planned Analysis

The main statistical model defined in the protocol does not include baseline response as a covariate, as baseline response is usually predictive of response the following changes to the protocol have been introduced:

- A sensitivity analysis of the primary efficacy endpoint has been included that includes baseline in an analysis of covariance (ANCOVA) model. Note the main analysis of the primary efficacy endpoint remains as defined in the protocol (i.e. without the addition of baseline as a covariate).
- The analysis of variance (ANOVA) model will be replaced by an ANCOVA model for all applicable exploratory endpoints in order to fit baseline response as a covariate.

2 Endpoints

Absolute change (Δ): will be defined as the value obtained at Week 12 minus value obtained at Baseline [$\Delta = \text{Week 12 (Value)} - \text{Baseline (Value)}$]. Positive value represents an increase from baseline. Negative value represents a decrease from Baseline.

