Safety criteria:	

• Adverse events (AE)

• AE of special interest (AESI)

• Incidence and intensity of AE including serious AE (SAE)

• Withdrawal from trial medication due to AE

• Clinically relevant new finding or worsening of existing condition on physical examination

• Clinically relevant changes in laboratory measurements from baseline

Statistical methods:	
The analysis will be performed on the per protocol set (PPS) of patients having a valid PCr/ATP ratio measurements available at baseline and at week 12, and not having an important protocol violation relevant to the primary endpoint.
 
Change from baseline of cardiac energetics (PCr/ATP ratio) at rest after 12 weeks of treatment will therefore be analysed by an analysis of variance (ANOVA) model. The model will include treatment, presence of atrial fibrillation at baseline (Yes/No) and history of diabetes (Yes/No) as fixed effects.
 
All planned analyses will be conducted separately on the two cohorts.

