## 7. STATISTICAL METHODS AND DETERMINATION OF SAMPLE SIZE

### 7.1 STATISTICAL DESIGN MODEL

This is a randomised, double-blind, single-centre placebo-controlled trial. The eligible patients for this trial will be randomised to empagliflozin 10 mg or placebo in a 1:1 ratio. Randomisation will be stratified by cohort (HFpEF / HFrEF) and history of diabetes (Yes / No).

The primary endpoint of change from baseline in cardiac energetics (PCr/ATP ratio) at rest is regarded as normally distributed based on literature data.

Change from baseline of cardiac energetics (PCr/ATP ratio) at rest after 12 weeks of treatment will therefore be analyzed by an analysis of variance (ANOVA) model. The model will include treatment, presence of atrial fibrillation at baseline (Yes / No) and history of diabetes (Yes / No) as fixed effects.

The analysis will be performed on the per protocol set (PPS) of patients having a valid PCr/ATP ratio measurements available at baseline and at week 12, and not having an important protocol violation relevant to the primary endpoint.

All planned analyses will be conducted separately on the two cohorts.

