### 7.3.1 Primary endpoint analyses

The patient set for the evaluation of cardiac energetics endpoints will be the PPS.

Change from baseline of cardiac energetics (PCr/ATP ratio) at rest after 12 weeks of treatment will be analyzed by an analysis of variance (ANOVA) model. The model will include treatment, history of atrial fibrillation and history of diabetes as fixed effects.

A sensitivity analysis will be conducted on the randomized set (ITT population). Subgroup analyses will be performed for the primary endpoint including subgroup analyses by history of diabetes and by eGFR (CKD-EPI)Cr at baseline (<60 vs ≥60 mL/min/1.73m^2).

For the subgroup analysis an ANOVA model as the primary will be conducted, additionally including the terms of the subgroup and subgroup by treatment interaction.

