3.1 Per-protocol Set (PPS)

The primary endpoint analysis will be performed using the per protocol (PP) set of patients having a valid PCr/ATP ratio measurements available at baseline and week 12, and not having an important protocol violation relevant to the primary endpoint. Protocol violations will be reviewed by the study team before the database lock to determine which violations disqualify a patient from the Per-Protocol analysis. A preliminary list of criteria that may disqualify a patient from the Per-Protocol analysis are presented in Section 9.2 in the SAP. The list is suggestive and subject to change at the final Blinded Report Planning Meeting (BRPM) pre-lock review.

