5.3 Primary Endpoint Analysis

5.3.1 Primary Efficacy Analysis

The primary efficacy endpoint of change from baseline to week 12 in PCr/ATP will be analysed for each cohort (HF_rEF and HF_pEF) separately, to test the hypothesis detailed in Section 2.1.2.

The analytical procedure will include a descriptive summary and a formal (inferential) statistical summary, ANOVA, for the primary endpoint hypothesis testing. Plots of individual patient changes from baseline to week 12 will be produced by treatment group and cohort, including the mean change also.

Formal analysis

The formal statistical analysis will employ an Analysis of Variance (ANOVA) model to test the primary hypothesis for each individual cohort using the following for the model inputs:

- Response (outcome) variable is defined as:
The change (PCr/ATP absolute change) from baseline to week 12 is calculated for each patient by subtracting each patient's baseline PCr/ATP measurement from the 12 weeks measurement.
- Factors:
Treatment (Empagliflozin vs. Placebo), History of diabetes (Yes/No) and History of atrial fibrillation (*Yes/No*)

The null hypothesis of no difference in change between the treatment and placebo groups will be tested by an ANOVA on the PCr/ATP ratio absolute change using treatment (empagliflozin vs. placebo), history of diabetes (yes vs, no) and history of atrial fibrillation (yes vs no) as fixed effects. If the treatment main effect is significant then we reject the null hypothesis.

[figure not shown]
The formal model will be specified in SAS as follows (equivalent to ANOVA):

```
PROC MIXED data=values cl method=reml covtest;  
CLASS af diab trt;  
MODEL endpt = af diab trt / ddfm=kr solution;  
LSMEANS trt / cl diff om alpha=0.05;  
RUN;
```

Though the primary endpoint is regarded to generally be normally distributed some model checking will be performed. The model adequacy assessment will be based on the normality of residuals, homogeneity of variance between groups and homoscedasticity. Any violation of the model assumptions will be investigated and ratified accordingly and will be reported in the clinical trial report.

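### The primary model in each cohort leaves out baseline PCr/ATP, although the SAP calls baseline response usually predictive and gives the adjusted model only a sensitivity role for this endpoint

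*SAP*

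**What the plan says.** The protocol synopsis says the change in resting PCr/ATP "will therefore be analysed by an analysis of variance (ANOVA) model". Protocol 7.1 says the same, and 7.3.1 lists the terms: "The model will include treatment, history of atrial fibrillation and history of diabetes as fixed effects". SAP 5.3.1 repeats this separately for each cohort, and its SAS code reads "MODEL endpt = af diab trt / ddfm=kr solution". Baseline PCr/ATP appears in none of these.

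SAP 1.4 addresses the omission directly. It gives the general reason for adjusting, "baseline response is usually predictive of response", and then makes two changes:

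- For the exploratory endpoints: "The analysis of variance (ANOVA) model will be replaced by an ANCOVA model for all applicable exploratory endpoints".
- For the primary endpoint, a baseline-adjusted ANCOVA is added as a sensitivity analysis only: "Note the main analysis of the primary efficacy endpoint remains as defined in the protocol (i.e. without the addition of baseline as a covariate".

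SAP 1.4 offers no reason for keeping the unadjusted model other than that it is the one in the protocol. SAP 4.2 allows one hypothesis per cohort on this single endpoint, and SAP 5.3.1 bases rejection on the ANOVA's treatment effect. Under SAP 3.1 the per-protocol set is made up of patients "having a valid PCr/ATP ratio measurements available at baseline and week 12", so every patient in the primary analysis has the covariate.

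**The concern.** The SAP's own argument for adjusting is applied to the main model of the exploratory endpoints but not to the main model of the one endpoint that carries a formal test. Each cohort's conclusion rests on about 15 evaluable patients per arm, and planned power is barely above 80%. Randomisation is stratified by cohort and diabetes, not by baseline PCr/ATP, so chance imbalance in baseline is left to the analysis model.

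If r is low or moderate, the sensitivity ANCOVA would have a tighter interval and a better chance of detecting the target effect, yet it could not supply the confirmatory p-value. If the two models disagreed, the one expected to be less precise would decide.

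**Working it through.** **Inputs.** From Protocol 7.7: effect 0.3, SD 0.28, two-sided 5% level per cohort, 30 evaluable and 43 randomised per cohort. From Protocol 7.6: 1:1 allocation, so 15 evaluable per arm. Not in the documents, so assumed: r, taken from 0.3 to 0.95, and equal variance at baseline and week 12. Protocol 7.7 does not say whether 0.28 is the SD of the change or of a single measurement. The main calculation takes it as the SD of the change; the other reading follows.

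**The plan's own figure.** A two-sample t-test with 15 per arm has power 80.8% (77.9% with 14). With diabetes and AF in the model, the residual df are 30 − 4 = 26 and power is 80.6%. Allowing for drop-out, 30/0.7 gives 43. The stated sample size is reproduced.

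**Residual variance.** With single-visit variance s²:

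- ANOVA on change: 2s²(1 − r)
- ANCOVA: s²(1 − r²)
- ratio ANCOVA/ANOVA: (1 + r)/2

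**Cost of estimating the baseline slope.** Chance baseline imbalance multiplies the variance of the ANCOVA treatment estimate by 1 + F/26, with F distributed as F(1, 26). Its mean is 1 + 1/24 = 1.042. The expected variance ratio is therefore 1.042 × (1 + r)/2. At r = 0.5 this is 1.042 × 0.75 = 0.78. Break-even is r = 2/1.0417 − 1 = 0.92.

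**Results.** Noncentral t power, ANOVA with 26 df, ANCOVA with 25 df and averaged over F:

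| r | Variance ratio | Power, effect 0.3 | Power, effect 0.2 | 95% CI half-width |
|---|---|---|---|---|
| ANOVA (any r) | 1 | 80.6% | 47.0% | 0.210 |
| 0.3 | 0.68 | 92.8% | 62.8% | 0.173 |
| 0.5 | 0.78 | 89.0% | 56.8% | 0.186 |
| 0.7 | 0.89 | 85.0% | 51.6% | 0.198 |
| 0.8 | 0.94 | 83.0% | 49.4% | 0.204 |
| 0.9 | 0.99 | 80.9% | 47.3% | 0.209 |
| 0.95 | 1.02 | 79.9% | 46.4% | 0.212 |

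**Simulation.** With 20,000 trials per value of r, diabetes-stratified allocation, both factors in both models, and assumed prevalences of 35% (diabetes) and 25% (AF), ANOVA power was about 79%. ANCOVA power was 92.0%, 87.9%, 83.7%, 81.4%, 79.6% and 78.3% at the same six values of r. Type I error, checked at r = 0.5, was 4.8% for both.

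**If 0.28 is the SD of a single measurement.** The SD of the change is then 0.28 × √(2(1 − r)), and power for 0.3 is:

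| r | SD of change | ANOVA | ANCOVA |
|---|---|---|---|
| 0.3 | 0.331 | 66.6% | 82.6% |
| 0.5 | 0.280 | 80.6% | 89.0% |
| 0.7 | 0.217 | 95.4% | 97.1% |

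**Chance imbalance.** With 0.28 again as the SD of the change, s = 0.28/√(2(1 − r)). A baseline difference of one standard error, s√(2/15), shifts the change-score estimate by (1 − r) times that difference. At r = 0.3, 0.5 and 0.7 the shift is about 0.06, 0.05 and 0.04, or 20%, 17% and 13% of the 0.3 target.

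**The case against.** This is a disclosed, prespecified choice and not an error. The ANOVA is unbiased under randomisation and holds its type I error. The sample size does not rely on adjustment, and the ANCOVA result will be reported anyway. All of that stands, and it limits the point to efficiency.

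The SAP's remark about baseline is also general, not specific to PCr/ATP. If it means that baseline predicts the week-12 value strongly, r is high and the gain is small: at r = 0.7 to 0.9, power is 85% to 81% against 80.6%. That stands too; the 93% figure needs r = 0.3.

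The break-even depends on equal variances. If the week-12 SD is k times the baseline SD, the variance ratio becomes 1.042 × k²(1 − r²)/(1 + k² − 2rk). Break-even falls to r of about 0.78 at k = 1.10 and 0.64 at k = 1.25. If k is below 1, the gain is larger than tabulated. This widens the uncertainty, but the downside is bounded. Since 1 + k² − 2rk = k²(1 − r²) + (1 − rk)², the ratio before the 1.042 factor never exceeds 1, so the expected loss of precision from adjusting is at most about 4% of variance for any k and r.

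Part of SAP 5.3 is blacked out, so a fuller rationale may exist there. That would not change which model decides.

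**Conclusion.** The point holds as a recommended improvement in efficiency; the planned analysis remains valid. Under equal variances, with 0.28 as the SD of the change and 15 per arm, adjusting for baseline adds about 12 points of power at r = 0.3, 8 at 0.5 and 4 at 0.7. The gain is close to nil at 0.9, and there is a loss of about 1 point at 0.95. If 0.28 is a single-measurement SD, the gain at r = 0.3 is 16 points. The documents give neither r nor the SD at each visit, so the size cannot be fixed more closely. The possible gain is much larger than the possible loss, and no patient is lost by adjusting.

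**What to change.** Before either cohort is unblinded, make the primary analysis in both cohorts an ANCOVA of change in resting PCr/ATP on baseline PCr/ATP, treatment, diabetes and AF. Amend the protocol synopsis, Protocol 7.1 and 7.3.1, and SAP 1.4 and 5.3.1, and add the baseline value to the MODEL statement. Keep the change-score ANOVA as the sensitivity analysis. The subgroup analyses in Protocol 7.3.1 are built on the primary model and should follow it.

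The cost is a protocol amendment with its approvals, matching SAP text, one model term and one residual degree of freedom. No new data or patients are needed. Timing matters because Protocol 4.1.5.1 allows the cohorts to be locked and unblinded separately, and the documents do not show whether either has been.

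If the ANOVA is kept as primary, SAP 1.4 should give the reason and the r assumed.

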2.1 Primary Endpoints

2.1.1 Definition and Derivation of Primary Endpoint

The primary endpoint is the change from the baseline to week 12 in PCr/ATP ratio in resting state measured by ^{31}P MRS after treatment with Empagliflozin or matching placebo.

2.1.2 Primary Hypothesis under Investigation

The null hypothesis is that for patients in each of the HF_rEF and HF_pEF cohorts, the change from the baseline to week 12 in PCr/ATP ratio in resting state measured by ^{31}P Magnetic Resonance Spectroscopy (MRS) after treatment with Empagliflozin is not different from matching placebo. The alternative hypothesis is that the change is different.

2.1.3 Handling of Outliers and Missing Data

For the primary outcome, patients who do not have a measurement taken at baseline and week 12 will be excluded from the primary analysis. For primary analyses, missing efficacy data will not be imputed.

Any outliers will be identified and documented prior to the database lock and unblinding. Cases that are visually “extreme” will be assessed for possible influence on the results and conclusions by comparing results from analyses with or without outliers. Any discrepant results from the two analyses will be reported and discussed in the CTR and publication manuscripts.

[figure not shown]
2.2 Secondary Endpoints

2.2.1 Definitions and Derivations of Secondary Endpoints

No secondary endpoints are defined for this trial.

2.2.2 Secondary Hypotheses under Investigation

No secondary hypotheses are defined for this trial.

3 Analysis Sets/Populations

The following analysis sets are defined in this trial.

3.1 Per-protocol Set (PPS)

The primary endpoint analysis will be performed using the per protocol (PP) set of patients having a valid PCr/ATP ratio measurements available at baseline and week 12, and not having an important protocol violation relevant to the primary endpoint. Protocol violations will be reviewed by the study team before the database lock to determine which violations disqualify a patient from the Per-Protocol analysis. A preliminary list of criteria that may disqualify a patient from the Per-Protocol analysis are presented in Section 9.2 in the SAP. The list is suggestive and subject to change at the final Blinded Report Planning Meeting (BRPM) pre-lock review.

3.2 Randomised Set (RS)

This set will include all subjects who are randomised to study treatment. The RS set will be employed for a sensitivity analysis to check for an unbiased estimation of the primary endpoint result if a substantial number of protocol violations resulted in a reduced sample size used for the primary endpoint estimates. The analysis of exploratory endpoints will be performed on the RS of patients with available data.

3.3 Treated set (TS)

All randomised and treated patients will be included in the safety analysis and safety summaries will be presented by actual treatment received.

4 General Issues for Statistical Analysis

Patients randomised into the incorrect stratum, cohort (HF_rEF or HF_pEF) and/or history of diabetes (Yes or No) will be analysed according to the stratum that they should have been randomised into.

The summary statistics and statistical estimates (effect sizes) will be presented to one decimal place greater than the raw data collected. All p-values will be rounded to 4 decimal places. All estimates of treatment effects will be presented with corresponding 95% confidence intervals.

For parameters which are known to follow a log-normal distribution (e.g. NT-proBNP and BNP), the geometric mean and geometric coefficient of variation will be used instead of the mean and standard deviation for any by visit descriptive summaries. Changes from baseline will be presented as geometric mean ratios.

4.1 Analysis Software

All statistical analyses will be conducted using SAS 9.4, software. All the statistical analyses outputs/results will be reviewed and validated by an independent DTU statistician.

4.2 Multiplicity, Multiple Comparisons and Interim Analyses

If recruitment is different between the cohorts such that one cohort's last patient out visit is considerably earlier than the last patient out of the other cohort, an interim analysis may be planned in order to report the data the completed cohort. For this interim analysis only the completed cohort will be unblinded.

A single hypothesis is being tested for each cohort for a single primary efficacy endpoint. The analysis of all other endpoints will be considered exploratory in nature with nominal p-values. All p-values will be two-sided at an alpha-level of 0.05.

5 Statistical Methodology

A table of contents for all outputs that will be produced along with supporting templates will be provided in separate documentation.

5.1 Disposition of Patients

All patients in the screened set (signed informed consent) will be included in the summary of patient disposition. Frequencies and percentages of the total number of patients screened, randomised, treated, prematurely discontinued treatment (along with reason for discontinuation) and status at trial completion will be summarised in tabular forms for each cohort and for both cohorts overall.

A summary of the frequency and percentage of patients by treatment group will be produced for the randomised, treated and per-protocol analysis sets. Summaries by cohort and overall will be produced.

5.2 Demographic and Baseline Characteristics

The screening demographic and the clinical characteristics will be tabulated and summarised by the treatment group. The demographic and baseline data will include gender, age, race, weight, height, SBP, DBP, T2DM, history of atrial fibrillation, alcohol use, smoking, heart rate, vital signs medical history, and other cardiac parameters (EF, BNP) measured at screening.

5.3 Primary Endpoint Analysis

5.3.1 Primary Efficacy Analysis

The primary efficacy endpoint of change from baseline to week 12 in PCr/ATP will be analysed for each cohort (HF_rEF and HF_pEF) separately, to test the hypothesis detailed in Section 2.1.2.

The analytical procedure will include a descriptive summary and a formal (inferential) statistical summary, ANOVA, for the primary endpoint hypothesis testing. Plots of individual patient changes from baseline to week 12 will be produced by treatment group and cohort, including the mean change also.

Formal analysis

The formal statistical analysis will employ an Analysis of Variance (ANOVA) model to test the primary hypothesis for each individual cohort using the following for the model inputs:

- Response (outcome) variable is defined as:
The change (PCr/ATP absolute change) from baseline to week 12 is calculated for each patient by subtracting each patient's baseline PCr/ATP measurement from the 12 weeks measurement.
- Factors:
Treatment (Empagliflozin vs. Placebo), History of diabetes (Yes/No) and History of atrial fibrillation (*Yes/No*)

The null hypothesis of no difference in change between the treatment and placebo groups will be tested by an ANOVA on the PCr/ATP ratio absolute change using treatment (empagliflozin vs. placebo), history of diabetes (yes vs, no) and history of atrial fibrillation (yes vs no) as fixed effects. If the treatment main effect is significant then we reject the null hypothesis.

[figure not shown]
The formal model will be specified in SAS as follows (equivalent to ANOVA):

```
PROC MIXED data=values cl method=reml covtest;  
CLASS af diab trt;  
MODEL endpt = af diab trt / ddfm=kr solution;  
LSMEANS trt / cl diff om alpha=0.05;  
RUN;
```

Though the primary endpoint is regarded to generally be normally distributed some model checking will be performed. The model adequacy assessment will be based on the normality of residuals, homogeneity of variance between groups and homoscedasticity. Any violation of the model assumptions will be investigated and ratified accordingly and will be reported in the clinical trial report.

5.4 Secondary Endpoint Analyses

Not applicable as no secondary endpoints defined for the study.

6 Safety and Tolerability Analysis

All safety and tolerability summaries will be produced on the treated set of patients.

6.1 Drug Exposure

Empagliflozin 10 mg for 12 weeks, see for the drug exposure and accountability plans throughout the trial (see also Protocol (1245.148) [Section 4.0](#)). Both empagliflozin and placebo exposure will be tabulated, duration of exposure will be calculated from the day of first exposure to the day of last exposure, ignoring any missed doses between. . Summaries of exposure by days and weeks will be produced. Cumulative dose (mg) will be summarized using descriptive statistics, where cumulative dose is the actual dose taken summed across all visits, missed days will be counted as 0 mg. The number of missed doses will also be tabulated.

